**Spinal sufentanil for relief of labor pain in primi- and multiparous parturients**

**NCT ID not yet assigned**

**Document Date: 05/29/2019**

## **1 INTRODUCTION**

Any parturient should be offered safe and effective analgesia at short notice during labor, and therapeutic options are pharmacological (nitrous oxide, non-opioid and opioid analgesics, regional and neuraxial nerve blocks) and non-pharmacological (hypnosis, biofeedback, intra- or subcutaneous sterile water injection, immersion in water, aromatherapy, relaxation techniques, acupuncture or acupressure, massage, transcutaneous electrical nerve stimulation) interventions . Neuraxial (epidural and/or spinal) nerve block is the most effective method of intrapartum pain relief in contemporary clinical practice . Intrathecal administration of local anaesthetic and/or opioid provides effective, although transient, pain relief during spontaneous vaginal delivery. However, although spinal opioid is being used more for obstetric analgesia, effects and adverse effects of intrathecal sufentanil alone for relief of labor pain have not been compared between primi- and multiparous parturients.

This descriptive study was designed to evaluate effects and potential adverse effects of spinal sufentanil for obstetrical pain relief in primi- and multiparous parturients.

## **2 MATERIAL AND METHODS**

### **2.1 Ethical approval**

The study design was approved by the regional Human Research Ethics Review Board, Lund, Sweden (Dnr 2015/687).

### **2.2 Study design and setting**

This descriptive study is based on retrospective data on obstetrical management of patients at the maternity ward of the Central Hospital in Kristianstad, Sweden, between 7th January 2013 and 29th July 2016.

### **2.3 Patients**

We included 164 (82 primi- and 82 multiparous) obstetrical patients given intrathecal sufentanil for labor pain. Demographic, obstetrical, and neonatal information in patients admitted to the maternity ward was obtained from the local obstetrical hospital database (ObstetrixTM, Cerner Sverige AB, Stockholm, Sweden).

### **2.4 Spinal analgesia**

Spinal analgesia (SA) was provided by a resident or specialist anaesthesiologist with the patient in a sitting or a recumbent position. A pencil-point needle, primarily 27 G (0.4 mm), otherwise 25 G (0.5 mm), was used for transdermal intrathecal administration of 2.0 ml of sufentanil 5 µg/ml (Sufenta®, Janssen-Cilag AB, Solna, Sweden) at low-lumbar level. Blood pressure was recorded before, immediately after, and at five-minute intervals for 20 minutes after the block. Any decrease in blood pressure by more than 30 % from the baseline level despite infusion of crystalloid was defined to indicate maternal hypotension.

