### **2.5 Study data**

Maternal demographics (age, height, weight, body mass index), obstetrical (medical history, gestational age, cervical dilation, progress of labor, indication and time for SA, hypotension, use of oxytocin, fetal bradycardia or late deceleration during the first hour after SA, supplementary analgesia, instrumental delivery, intrapartum Cesarean section (CS), third- or fourth-degree perineal tear, maternal satisfaction with pain relief, postdural puncture headache, use of epidural blood patch), and neonatal (time of birth, fetal heart rate (FHR), Apgar score, weight at birth, use of neonatal intensive care, feeding) data was obtained as reported above.

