### **2.6 Statistical analysis**

A total sample size of 150 parturients had been calculated to enable differences of at least 20 % versus 5.0 % in proportions of obstetrical and neonatal problems between (equal numbers of) primi- and multiparous mothers to be statistically confirmed with 80 % power and 95 % probability.

Descriptive parametric data is reported as mean  $\pm$  standard deviation (SD), and proportions in percent with 95 % confidence interval (CI).

Parametric data was compared with two-tailed unpaired student's t-test, and proportions analyzed with Fisher's exact test.

Probability (*P*) values  $< 0.05$  were considered statistically significant.

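### Six blood pressure readings per woman are reduced to one yes/no at a 30 % fall, so the parity comparison of blood pressure response is less efficient than the recorded data allow

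*Combined protocol and SAP*

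**What the plan says.** Section 2.4 (Spinal analgesia) sets out the measurement schedule: "Blood pressure was recorded before, immediately after, and at five-minute intervals for 20 minutes after the block". This gives six readings: before the block, immediately after it, and at 5, 10, 15 and 20 minutes. The same section builds the hypotension definition on them: "Any decrease in blood pressure by more than 30 % from the baseline level", with the added condition that the fall occurs despite crystalloid.

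Section 2.5 (Study data) lists one maternal haemodynamic variable, hypotension, within the run "indication and time for SA, hypotension, use of oxytocin". It lists no pre-block value, lowest value or change.

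Section 2.6 (Statistical analysis) assigns proportions to Fisher's exact test and parametric data to a two-tailed unpaired t-test. As no blood pressure value is listed in 2.5, none reaches the t-test. The study is sized on proportions: "A total sample size of 150 parturients had been calculated" to show "differences of at least 20 % versus 5.0 % in proportions of obstetrical and neonatal problems", "with 80 % power and 95 % probability". Section 2.3 gives the number analysed: "We included 164 (82 primi- and 82 multiparous) obstetrical patients".

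**The concern.** The study aims to describe effects and adverse effects of the block by parity. Blood pressure is the one listed response that the text describes as measured in the same woman before the block and repeatedly after it, on a continuous scale. Cutting it at a 30 % fall treats a woman with a 29 % fall like one with no fall at all. If few women cross the cut, most of the information on whether blood pressure response differs by parity is discarded. A Fisher result with P above 0.05 could then come from a comparison that had little chance of detecting a moderate difference.

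The point concerns the dichotomy only, not the crystalloid wording in the definition.

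**Working it through.** **Inputs from the documents.** 82 women per group (2.3); planned total 150 in equal groups, 20 % v 5 %, 80 % power, 5 % significance level read as two-sided (2.6); cut at a 30 % fall (2.4). Fisher's test is taken as two-sided.

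**Inputs assumed.** The documents give no expected hypotension rate, mean fall or SD. The scenarios take each woman's maximum percentage fall as normal, with equal SD in both groups and parity acting as a pure shift in the mean. The crystalloid condition is ignored.

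**Step 1: the plan's own figure.** Pooled two-proportion formula with mean rate 0.125:

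n per group = [1.96 × √(2 × 0.125 × 0.875) + 0.842 × √(0.20 × 0.80 + 0.05 × 0.95)]² / 0.15² = 75.1, rounded up to 76, or 152 in total.

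This agrees with the stated 150; power at 75 per group is 79.9 %. With the 82 per group included, power for 20 % v 5 % is 83.4 % by normal approximation and 80.5 % by exact Fisher enumeration.

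**Step 2: yes/no against continuous at the plan's own effect.** On a normal scale, 20 % v 5 % beyond a common cut is a shift of z(0.95) − z(0.80) = 1.645 − 0.842 = 0.80 SD. With 82 per group, noncentral-t power for that shift is 99.9 %, against 80.5 % for Fisher.

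**Step 3: smaller shifts and lower rates.** P(fall > 30) = 1 − Φ((30 − mean)/SD). For means of 12 and 17 with SD 10:
- 1 − Φ(1.8) = 3.6 %
- 1 − Φ(1.3) = 9.7 %

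Exact Fisher power against t-test power, 82 per group:

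| Mean falls (%), SD | Rates above 30 % | Fisher | t-test |
|---|---|---|---|
| 10 v 15, SD 10 | 2.3 v 6.7 % | 14 % | 89 % |
| 12 v 17, SD 10 | 3.6 v 9.7 % | 23.5 % | 89 % |
| 15 v 20, SD 10 | 6.7 v 15.9 % | 38 % | 89 % |
| 20 v 25, SD 10 | 15.9 v 30.9 % | 56 % | 89 % |
| 25 v 30, SD 10 | 30.9 v 50.0 % | 65 % | 89 % |
| 12 v 17, SD 8 | 1.2 v 5.2 % | 12 % | 98 % |
| 12 v 17, SD 12 | 6.7 v 13.9 % | 26 % | 76 % |
| 12 v 17, SD 15 | 11.5 v 19.3 % | 22 % | 56 % |
| 12 v 17, SD 20 | 18.4 v 25.8 % | 16 % | 36 % |

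The t-test column does not change across the first five rows because each is a 0.5 SD shift.

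**Step 4: information kept by the cut.** For small shifts, the efficiency of the dichotomy relative to the continuous measure is φ(z_p)² / [p(1 − p)], where p is the hypotension rate:
- 5 %: 0.1031² / 0.0475 = 0.22
- 12.5 %: 0.2059² / 0.1094 = 0.39
- 50 %, the best case: 0.3989² / 0.25 = 0.64

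**Step 5: a case against the mean-shift model.** Let one group be N(12, 10), and let the other be the same except that 15 % of its women are drawn from N(35, 4). The rates above 30 % are then 3.6 % and 0.85 × 3.6 % + 0.15 × 89.4 % = 16.5 %. Fisher has about 75 % power and the t-test about 49 % (simulated).

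The t-test on the maximum fall stands in here for a baseline-adjusted analysis. The further gain from adjustment cannot be computed, because no correlation between pre-block and post-block readings is given.

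**The case against.** A reader might infer that the dichotomy costs most of the power as a general result. The documents do not support that. At the only effect the plan specifies, Fisher keeps 80.5 % power and meets the target. Where falls above 30 % are common, it keeps 56 to 65 % against 89 %. If parity affects only a susceptible minority, the ranking reverses (step 5). With SD 15 or 20 and a five-point shift, the continuous test is itself underpowered. All of this stands, and it limits the claim to a loss of efficiency whose size is unknown.

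A reader might also infer that the continuous measure should replace hypotension as the tested outcome. That does not follow either. A fall above 30 % despite crystalloid is a legitimate adverse event and a different question from a mean difference in falls that mostly stay below the cut. Post-block readings may also have been modified by crystalloid, so a continuous comparison does not isolate the effect of the block. The Fisher test should stay.

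Two further objections stand in part:
- The data are retrospective (2.2) and come from a hospital database (2.3). Section 2.4 says readings were recorded, not that each value can be retrieved, so the remedy must be conditional.
- Section 2.6 reports proportions with 95 % confidence intervals, which shows imprecision, and nothing in the plan says that a non-significant result will be read as no difference. This softens the risk of misreading but does not recover the lost information.

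**Conclusion.** The point holds as a loss of efficiency. Six readings are described, the hypotension definition depends on them, and no analysis of the size of the fall is planned. The loss is severe if hypotension is uncommon and the shift modest: about 24 % v 89 % power for mean falls of 12 % v 17 % with SD 10. At the plan's own 20 % v 5 % it is much smaller, 80.5 % v 99.9 %, and has little practical consequence. These are scenarios, not predictions. They rest on a normal fall, equal SDs and a pure mean shift, and the documents offer no rate, mean or SD with which to choose among them. Nothing here questions the sample size or the use of hypotension as an adverse-event outcome.

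**What to change.** Where the individual readings can be retrieved:

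- **Section 2.5:** add the pre-block reading and the lowest of the post-block readings within 20 minutes, using the same blood pressure component for every woman.
- **Section 2.6:** add a parity comparison of the lowest reading adjusted for the pre-block reading (ANCOVA), reporting the adjusted difference and its 95 % CI. Present it alongside hypotension yes/no with its Fisher test.
- **Reporting:** state, by parity group, how many women lack readings, and note that post-block values may reflect crystalloid.

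If the readings cannot be retrieved, say so as a limitation and give the parity difference in hypotension with its 95 % CI.

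The cost is a few sentences of text and transcription for up to 164 women if the values are not already in the data file. Some readings will probably be missing, possibly not at random. No new patients are needed.

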### **2.5 Study data**

Maternal demographics (age, height, weight, body mass index), obstetrical (medical history, gestational age, cervical dilation, progress of labor, indication and time for SA, hypotension, use of oxytocin, fetal bradycardia or late deceleration during the first hour after SA, supplementary analgesia, instrumental delivery, intrapartum Cesarean section (CS), third- or fourth-degree perineal tear, maternal satisfaction with pain relief, postdural puncture headache, use of epidural blood patch), and neonatal (time of birth, fetal heart rate (FHR), Apgar score, weight at birth, use of neonatal intensive care, feeding) data was obtained as reported above.

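### Does supplementary analgesia need a stated time window and a planned block-to-birth interval before it is compared by parity?

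*Combined protocol and SAP*

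**What the plan says.** Section 1 (Introduction) says that intrathecal local anaesthetic and/or opioid "provides effective, although transient, pain relief during spontaneous vaginal delivery", and that this descriptive study was "designed to evaluate effects and potential adverse effects of spinal sufentanil for obstetrical pain relief in primi- and multiparous parturients". No duration of relief is given.

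Section 2.5 (Study data) lists the items taken from the hospital database. In the obstetrical list stands "fetal bradycardia or late deceleration during the first hour after SA, supplementary analgesia, instrumental delivery". The window belongs to the fetal item; supplementary analgesia follows without one. The same section collects "indication and time for SA" and, under neonatal data, "neonatal (time of birth, fetal heart rate (FHR), Apgar score", so the two ends of the SA-to-birth interval appear to be available. It also lists cervical dilation, progress of labor and "maternal satisfaction with pain relief".

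Section 2.6 (Statistical analysis) has "proportions analyzed with Fisher's exact test", a two-tailed unpaired t-test for parametric data, and a 0.05 significance level. It assigns no individual item to a test and plans no adjustment or time-to-event method. Section 2.3 gives 82 primiparous and 82 multiparous women.

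**The concern.** If relief wears off, the chance of ever receiving a supplement rises with the time a woman remains undelivered after the block. A yes/no count over an unstated period then mixes two things: how well or how long the block works, and how long it is asked to work. If primiparous and multiparous women differ in SA-to-birth time, Fisher's test can be significant with identical need per hour in both groups.

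The contrast within section 2.5 makes the gap conspicuous, since the neighbouring item has an explicit window. Section 1 speaks of evaluating effects by parity, so a significant P value could be read as weaker or shorter analgesia in one group. Nothing obliges the authors to print the SA-to-birth interval beside the proportion, so a reader might be unable to tell the two explanations apart.

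**Working it through.** **The plan's own figure.** Section 2.6 gives a total of 150 for 20 % versus 5 %, 80 % power, 5 % significance (taken as two-sided) and equal groups. With pooled proportion 0.125:

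n per group = [1.96·√(2·0.125·0.875) + 0.8416·√(0.20·0.80 + 0.05·0.95)]² / 0.15² = (0.9167 + 0.3834)² / 0.0225 = 75.1, rounded up to 76, or 152 in total.

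Power at 75 per group is 79.9 %, so the figure reproduces. Exact Fisher power for the same rates is 76.0 % at 75 per group and 80.5 % at the 82 per group included. The present point does not touch the sample size.

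**How far time at risk alone could move the test.** From the documents: 82 per group, Fisher's exact test, 0.05. Assumed, because the documents give no values:

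- SA-to-birth times are exponential with mean T.
- No requests occur for a period L after the block; requests then arise at rate h per hour.
- L and h are the same in both parity groups.

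Then

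P(supplement before birth) = exp(−L/T) · h / (h + 1/T).

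Example with L = 1.5 h and h = 1 per hour:

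- T = 3 h: exp(−0.5) · 1/(1 + 1/3) = 0.6065 · 0.75 = 45.5 %.
- T = 2 h: exp(−0.75) · 1/(1 + 1/2) = 0.4724 · 0.6667 = 31.5 %.

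Enumerating all outcomes of two groups of 82, the two-sided Fisher test rejects with probability 38.5 %. Over the grid:

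| Mean SA-to-birth time, h | L = 0, h = 0.1 to 0.3 per hour | L = 1 to 2 h, h = 0.5 or 1 per hour |
|---|---|---|
| 2 vs 2 | 3.0 % to 3.3 % | 3.0 % to 3.4 % |
| 2 vs 1.5 | 6.6 % to 10.7 % | 17.9 % to 22.1 % |
| 3 vs 2 | 12.8 % to 19.7 % | 32.8 % to 42.7 % |
| 4 vs 2 | 37.5 % to 53.2 % | 75.7 % to 86.5 % |

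The mechanism is real. Every entry above 5 % comes from an assumed inequality in SA-to-birth time; with equal times the test stays near 3 %.

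**What these rejections mean.** They are false positives only for the hypothesis of equal need per hour. In the 45.5 % versus 31.5 % example the groups do differ in how often one block failed to last until birth, and rejecting equality of those proportions is correct. The test is wrong only if its result is relabelled as a difference in analgesic effect.

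**Does the plan do that relabelling?** Set side by side:

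- Section 2.5 places supplementary analgesia among obstetrical items and names it neither as an efficacy measure nor as a marker of duration.
- Section 2.6 sizes the study on obstetrical and neonatal problems.
- Sections 1 and 2.2 call the study descriptive.
- Section 2.5 has a more direct item on effect, "maternal satisfaction with pain relief".

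**Can the interval be had within the plan?** If the time recorded for SA is its clock time, SA-to-birth time is the difference of two collected items, and mean ± SD with a t-test is already the method for such a variable.

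**The case for a change.** The strongest case for a change is that section 2.6 plans tests at P < 0.05, whatever the study calls itself, and that modest gaps in time suffice. From a shorter mean of 2 h, under the same assumptions, rejection passes 5 % once the means differ by 0.19 to 0.44 h and 10 % at 0.39 to 0.84 h. The remedy is cheap: one definition, one table row, one cautionary sentence. And with "intrapartum Cesarean section (CS" among the collected items, one can ask whether anaesthesia given for it counts as a supplement.

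The arithmetic stands, and so does the caution about interpretation. The rest is weaker. Supplementary means after the block, and labor analgesia ends at birth, so few analysts would choose another window; oxytocin use, instrumental delivery and perineal tears carry no window either. The item says analgesia, so counting anaesthesia for surgery would be a strained reading. That nothing guarantees the interval is printed holds for every variable, since section 2.6 assigns none to a test; this is brevity, not a specific error. If parity acts on supplement use through time to birth, that is part of the parity difference a descriptive study may legitimately report.

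Heavier methods offer no clear gain. Time to first supplement, censored at birth, needs a time that section 2.5 does not list and assumes that need is unrelated to closeness to birth. Adjusting for SA-to-birth time conditions on something that happens after the block.

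**Conclusion.** No change to the plan is called for. The window is unstated and the SA-to-birth interval is not named, but analysts would fill both gaps sensibly from data apparently in hand and with methods already listed. Followed as written, the plan yields a correct description of how often one block did not suffice until birth.

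The possible distortion concerns only a reading that the documents do not make. Its size is unknown: about 3 % rejection with equal times, 7 % to 22 % at 2 versus 1.5 h, and up to 87 % at 4 versus 2 h, all resting on assumed exponential times, assumed request rates and identical need in both groups. It touches one outcome among many and leaves the sample size alone.

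As a matter of reporting, it would help to show the derived interval by parity beside the proportion and not to take the crude result alone as a parity difference in analgesic effect. This conclusion assumes that the recorded time for SA is a clock time, and that supplementary analgesia is coded ever or never between SA and birth.

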### **2.6 Statistical analysis**

A total sample size of 150 parturients had been calculated to enable differences of at least 20 % versus 5.0 % in proportions of obstetrical and neonatal problems between (equal numbers of) primi- and multiparous mothers to be statistically confirmed with 80 % power and 95 % probability.

Descriptive parametric data is reported as mean  $\pm$  standard deviation (SD), and proportions in percent with 95 % confidence interval (CI).

Parametric data was compared with two-tailed unpaired student's t-test, and proportions analyzed with Fisher's exact test.

Probability (*P*) values  $< 0.05$  were considered statistically significant.

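### The 80 % power stated for 150 women is 76 % under a two-sided Fisher's exact test; the 164 women included give 80.5 %

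*Combined protocol and SAP*

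**What the plan says.** Section 2.6 (Statistical analysis) contains the plan's only power statement. It reads "A total sample size of 150 parturients had been calculated to enable differences of at least 20 % versus 5.0 % in proportions". The outcomes meant are problems in the mother or the newborn, the two parity groups are taken to be of equal size, and the difference is "to be statistically confirmed with 80 % power and 95 % probability". It does not give the formula behind 150.

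The same section then fixes the tests: "Parametric data was compared with two-tailed unpaired student's t-test, and proportions analyzed with Fisher's exact test". The significance threshold is P below 0.05. The sidedness is stated for the t-test and not for Fisher's test.

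Section 2.3 (Patients) reports the number obtained: "We included 164 (82 primi- and 82 multiparous) obstetrical patients given intrathecal sufentanil for labor pain".

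**The concern.** Power is a property of a design together with the test applied to it. The outcomes covered by the calculation are proportions, and Fisher's exact test is the only test the plan names for proportions. A reader will therefore take 150 women as enough for 80 % power with Fisher's test.

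Fisher's test is conservative at these sample sizes, so a size derived from a normal approximation normally falls short when the data are analysed with it. If that happened here, the stated 80 % at 150 is too high, and the plan gives no power for the 164 women actually analysed. At stake is the accuracy of the sample-size justification, not the validity of the comparisons themselves.

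**Working it through.** **Inputs.** From section 2.6: p₁ = 0.20, p₂ = 0.05, equal groups, total 150 (n = 75 per group), power 80 %, α = 0.05 (from the 95 % probability and the P threshold), Fisher's exact test for proportions. From section 2.3: 164 included (n = 82 per group). Assumed: Fisher's test is two-sided.

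**Step 1. Reproduce 150.** The uncorrected two-sided normal formula with pooled variance under the null is

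n = [z₀.₉₇₅ √(2p̄(1 − p̄)) + z₀.₈₀ √(p₁(1 − p₁) + p₂(1 − p₂))]² / (p₁ − p₂)²

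with p̄ = (0.20 + 0.05)/2 = 0.125.

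- First term: 1.960 × √(2 × 0.125 × 0.875) = 1.960 × √0.21875 = 0.917
- Second term: 0.8416 × √(0.16 + 0.0475) = 0.8416 × √0.2075 = 0.383
- n = (0.917 + 0.383)² / 0.15² ≈ 1.690 / 0.0225 = 75.1 per group

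This is about 150 in total, or 152 if each group is rounded up to 76. The approximate power at 75 per group is 79.9 %, so the plan's figure is reproduced.

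Other formulas fit less well:

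| Formula | Total |
|---|---|
| Two-sided, pooled, uncorrected | about 150 (75.1 per group) |
| Two-sided, unpooled | 146 (72.4 per group) |
| Two-sided, arcsine | 140 (69.2 per group) |
| Two-sided, continuity-corrected | 176 |
| One-sided 5 %, pooled, uncorrected | 120 (59.1 per group) |
| One-sided 5 %, continuity-corrected | 144 |

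**Step 2. Exact power of Fisher's test.** Let X₁ ~ Bin(n, 0.20) and X₂ ~ Bin(n, 0.05) be independent. Then

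power = Σ Σ Pr(X₁ = a) Pr(X₂ = b) × 1{Fisher P(a, b) < 0.05}

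summed over all a, b from 0 to n. The two-sided P value adds the probabilities of all tables no more probable than the observed one. Doubling the one-sided P value gives the same power at 75 and at 82 per group.

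| n per group | Total | Two-sided Fisher power |
|---|---|---|
| 73 | 146 | 74.5 % |
| 75 | 150 | 75.96 % |
| 76 | 152 | 76.7 % |
| 78 | 156 | 78.0 % |
| 80 | 160 | 79.3 % |
| 81 | 162 | 79.93 % |
| 82 | 164 | 80.53 % |

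The shortfall at 150 is 80 − 75.96 = 4.0 points. Power first reaches 80 % at 82 per group.

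**Step 3. Is the test the cause?** The same enumeration with an uncorrected chi-square test gives 82.7 % at 75 per group, so the loss comes from using Fisher's test. Its actual type I error at 75 per group is at most 0.041 over common null rates from 1 % to 50 %, against a nominal 0.05.

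**Step 4. What 150 women can detect.** At 75 per group, two-sided Fisher power reaches 80 % at about 20.9 % versus 5 %, not at 20 % versus 5 %.

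**Step 5. Sensitivity to sidedness.** A one-sided Fisher's test at 0.05 would give 85.1 % at 75 per group and 87.4 % at 82.

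**The case against.** The numbers are not in dispute; their weight is. Five points can be made for the plan.

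- **Nothing in the study changes.** The data are retrospective (section 2.2) and the sample is fixed. The 82 per group included is exactly the size at which two-sided Fisher power reaches 80 %. This stands, and it keeps the matter minor.
- **The plan never says the 80 % was computed for Fisher's test.** As a normal-approximation result it is correct, so 150 is not an arithmetic slip. That is true. But no formula is given, and a reader has only the named test to attach the figure to.
- **The sizing formula is inferred.** The pooled formula gives 75.1, which strictly rounds up to 76 per group. This is fair as to where 150 came from, but the 76 % follows from the plan's own rates, sizes and test whichever formula was used.
- **The 76 % depends on a two-sided test.** Under a one-sided test there is no shortfall. Two-sided is the better reading: it matches the t-test, and the one-sided formulas give 120 or 144, not 150. Neither reading yields 80 % at 150.
- **The margin at 164 is thin.** It is half a point, and 81 per group already falls to 79.93 %. The data come from a routine hospital database and section 2.6 does not address missing values. This also stands: the 80.5 % should be stated as conditional on complete data.

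It can be added that the study calls itself descriptive and ties the 20 % versus 5 % contrast to no named outcome. That limits how much a 4-point correction tells anyone about a particular outcome, but it does not make the stated figure right.

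**Conclusion.** The concern holds. For 20 % versus 5 % at P < 0.05, a two-sided Fisher's exact test on 150 women has 76.0 % power, not 80 %. The 164 included have 80.5 %. The stated power is 4 points too high at the planned size, while the sample achieved meets the target.

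This rests on equal groups, independent binomial outcomes, a two-sided test (assumed) and, for the 164, complete outcome data. It is a low-priority reporting correction and no evidence that the study as carried out falls below its power target.

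**What to change.** In section 2.6, keep the record of the calculation for 150, name the formula used if it is known, and add a clarification such as:

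> *With a two-sided Fisher's exact test at a significance level of 0.05, 150 parturients give 76 % power for 20 % versus 5 %; the 164 included (82 per group) give 80.5 % if outcome data are complete.*

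Label it as computed after the sample was obtained. In the sentence naming the tests, write two-sided before Fisher's exact test, provided the sponsor confirms that this was the test used. Retain Fisher's test.

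The cost is one sentence and one word, with no more patients and no change of analysis. The only downside is a slightly less favourable power figure at 150.

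### Does Section 2.6 need to say which test applies to Apgar score, cervical dilation, progress of labor and maternal satisfaction?

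*Combined protocol and SAP*

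**What the plan says.** Section 2.6 recognises two classes of data. For the first, "Descriptive parametric data is reported as mean" with SD; for proportions it gives a percentage with a 95% confidence interval. The tests follow the same split: "Parametric data was compared with two-tailed unpaired student's t-test, and proportions analyzed with Fisher's exact test". The significance threshold is 0.05 throughout.

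Section 2.5 lists the variables taken from the obstetrical database. Among them are "gestational age, cervical dilation, progress of labor, indication and time for SA", then "maternal satisfaction with pain relief", and on the neonatal side "fetal heart rate (FHR), Apgar score, weight at birth, use of neonatal intensive care, feeding". None of Apgar score, cervical dilation, progress of labor and satisfaction is assigned to a class. Progress of labor and satisfaction have no stated scale, and Apgar score has no time point or cut-off.

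Other items are defined more tightly. Section 2.4 gives an explicit threshold for low blood pressure: "Any decrease in blood pressure by more than 30 % from the baseline level despite infusion of crystalloid was defined to indicate maternal hypotension". Section 2.2 describes the setting: "This descriptive study is based on retrospective data on obstetrical management of patients".

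**The concern.** Apgar score and cervical dilation are bounded whole-number scales, and Apgar scores may pile up at the top. Progress of labor and satisfaction could each be a category, a score, a rate or a time. If a variable may be analysed either as a mean or as a proportion at some cut-off, two analysts could reach different P values from the same records. The data run from 2013 to 2016 and the document is dated 2019, so nothing in the text shows that these choices were made before the values could be seen.

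Two things would be at stake: the false-positive rate, if the choice followed the result, and the quality of description, if mean and SD were used for a strongly skewed variable.

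**Working it through.** **1. The plan's own figure.** Inputs from Section 2.6: 20% versus 5%, 80% power, two-sided 0.05, equal groups. With the mean proportion 0.125 and the pooled normal formula,

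n = [1.96·√(2·0.125·0.875) + 0.8416·√(0.20·0.80 + 0.05·0.95)]² / 0.15² = (0.9167 + 0.3834)² / 0.0225 = 75.1 per group.

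That is 150 in total before rounding up (152 after), so the stated 150 reproduces. Section 2.3 gives 82 per group, where exact power for Fisher's test is 80.5%. None of this involves the four variables in question.

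**2. Is each available analysis valid?** The documents give no distributions, so these are assumptions. Apgar 3 to 10 has probabilities 0.01, 0.01, 0.01, 0.02, 0.03, 0.07, 0.35, 0.50. Dilation 2 to 10 has 0.03, 0.08, 0.15, 0.20, 0.18, 0.14, 0.11, 0.07, 0.04. Each simulation uses 82 per group, a two-sided 0.05 level and 20,000 runs (10,000 for Mann-Whitney). With no true difference:

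| Analysis | Apgar-like | Dilation-like |
|---|---|---|
| t-test alone | 5.1% | 5.0% |
| Fisher alone, below 7 / 8 / 9 | 1.5% / 2.6% / 3.1% | not run |
| Smaller P of t-test and Fisher below 7 | 5.8% | not run |
| Smallest P of t-test and three Fisher cut-offs | 8.0% | 9.5% |

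The dilation cut-offs were below 5, 6 and 7. Repeat simulations of the last row gave 7.6% and 8.2% for Apgar and 9.7% and 10.0% for dilation. With fewer or more low Apgar scores it was 7.2% and 8.4%. Any single choice is therefore valid, and only taking the best of four raises the rate.

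**3. Would a different rule do better?** Two Apgar alternatives were compared with the base distribution.

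*Low-tail difference* (0.03, 0.03, 0.03, 0.04, 0.04, 0.07, 0.31, 0.45). The means are 9.16 and 8.73 and the variances 1.614 and 3.277, so SE = √[(1.614 + 3.277)/82] = 0.244. The ratio is 0.43/0.244 = 1.76, and power is about Φ(1.76 − 1.96) = 42%. Simulation gave 41%. Below 7 the proportions are 5% and 13%, for which Fisher's power is 34%. Mann-Whitney gave 21%.

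*Shift from 10 to 9* (0.55 at 9, 0.30 at 10, the rest unchanged). The means are 9.16 and 8.96 and the variances 1.614 and 1.438, so SE = 0.193. The ratio is 0.20/0.193 = 1.04 and power about 18%. Simulation gave 19%. Below 7 both groups stand at 5%, so Fisher rejects only at its null rate of about 2%. Mann-Whitney gave 54%.

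*Dilation*, against 0.02, 0.05, 0.11, 0.17, 0.19, 0.17, 0.14, 0.09, 0.06. The means are 5.87 and 6.34 and the variances 3.833 and 3.764, so SE = 0.304. The ratio is 1.54 and power about 34%. Simulation gave 34% for the t-test and 35% for Mann-Whitney.

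Fisher at one Apgar cut-off loses to the t-test in both scenarios. A rank test wins one and loses the other. For dilation the choice makes no practical difference.

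**The case for a change.** The strongest case for a change is that convention does not settle every variable. Dilation would ordinarily go to the t-test. Apgar score could reasonably be a mean or a proportion of low scores, and the second is close to the yes/no problems that the sample size was built on, so a cut-off would define the outcome. Satisfaction and progress of labor cannot be classified at all without their scale. The authors fixed a threshold for hypotension and could have done the same here. A short table would cost nothing and alter no stated figure.

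The omission stands as a fact. It does not follow that the results would be unsound. Section 2.5 is a list of data collected, alongside items such as height and medical history, and is not a list of endpoints. The study calls itself descriptive, names no primary outcome, and ties no conclusion to a P value for any of these four variables. If satisfaction and progress of labor were stored as categories, percentages and Fisher's test already cover them; the document does not state their format. Advice on skewed times would apply only if a labor duration is compared, which the document does not say. The point about undocumented timing of choices also stands, but a table written after data collection cannot show that they were made in advance.

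**Conclusion.** No change to the plan follows. Section 2.6 supplies a summary and a valid test for each of its two classes, and an analyst can place each of the four variables sensibly once its recorded format is known. Any one fixed choice keeps the false-positive rate at or below about 5% at 82 per group. The worst case, about 7% to 10%, needs deliberate selection across four analyses and rests on assumed distributions; with a single possible cut-off it is about 5% to 7%. The document gives no sign of such selection.

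The alternatives bring no clear gain: a fixed Apgar cut-off below 7 lowers power relative to the t-test in both scenarios, and for dilation the t-test and rank test are equivalent. Mean and SD could describe a ceiling-bound score poorly, but the remedy for that is to report the scale, time point and summary actually used. The sample size of 150 and the 82 per group included are untouched.
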